5.2 Overall Study Design

This is an open-label phase Ib trial of avelumab and intravesical BCG in patients with NMIBC. The study will utilize a modified 3+3 design for potential dose de-escalation in case of patients cannot tolerate to a full dose intravesical BCG. In order to adequately assess safety data at the conclusion of this combination therapy, 3~6 patients will be enrolled at starting dose level (dose level 1). Dose limiting toxicity will be based on the first 6 weeks of proposed study treatment. If 0/3 patients experience a DLT, dose expansion cohort will be activated for additional 15 patients. If 1/3 patients experiences a DLT, the dose level 1 will be expanded to 3 more patients. If 1/6 patients experiences a DLT, the dose expansion cohort will be activated for additional 12 patients. If 2 or more of the 6 patients experience a DLT, the dose level -1 will be evaluated.

At the dose level 1, 3~6 patients will be enrolled to evaluate the safety of proposed combination therapy with standard BCG dosing (50 mg) plus avelumab (10 mg/kg, IV weekly during BCG and every two weeks between BCG). The ability of patients to receive a complete induction course of combination therapy is defined as 5 of 6 weekly treatments of BCG with weekly infusion of avelumab within an 8 week period. Patients will continue maintenance therapy if they tolerate the induction course. Eligible patients will receive avelumab 10 mg/kg, IV weekly dosing plus intravesical BCG 50 mg weekly, 6 weeks on, then 6 weeks off during induction and will continue on a standard maintenance regimen with combination therapy for 1 year. Maintenance therapy beyond 1 year will be at the discretion of the treating physician and will be BCG monotherapy.

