5.2.1 Definition of Dose limiting toxicity

During safety lead-in phase, Dose limiting toxicity (DLT) will be monitored during the first 6 weeks of the combination avelumab and intravesical BCG. DLTs will be defined as any and all adverse events at least possibly related to study drug which occur in the DLT evaluation period and meet the criteria below, as evaluated by the NCI-CTCAE version 5.0.

Note: DLTs and other toxicities will be discussed between the Principal Investigator, and the Data Safety Monitoring Committee (DSMC). The discussions are the basis for the decisions regarding dose expansion (or de-escalation) according to the rules of the protocol.

DLT will be classified as either hematologic or non-hematologic toxicity (assessed in accordance with the CTCAE Version 5.0 criteria).

The following are DLTs:

1. Toxicity causing greater than 2 weeks of dose delay. For example, if a subject has dose delay greater than 2 weeks due to an AE, such AE is a DLT.
2. Grade 4 neutropenia greater than 5 days.
3. ALT/AST $> 3x$ ULN with bilirubin $> 2x$ ULN without another explanation (e.g., cholestasis)
4. Any Grade 3 hypersensitivity reaction is a DLT
5. Grade 4 thrombocytopenia of any duration
6. Grade 3 thrombocytopenia with significant hemorrhage of any duration
7. Febrile neutropenia

And, any non-hematological Grade ≥ 3 toxicities will be a DLT.

The following may be considered as exceptions to DLTs:

1. Grade 3 nausea, vomiting, or diarrhea and Grade 4 vomiting or diarrhea in the absence of maximal medical therapy that resolves in 72 hours
2. Grade 3 fatigue lasting < 5 days
3. Grade 3 hypertension that can be controlled with medical therapy
4. An increase of indirect (unconjugated) bilirubin indicative of Gilbert's syndrome
5. Serum lipase and/or serum amylase CTCAE Grade 3 ≤ 7 consecutive days without clinical signs or symptoms of pancreatitis

5.2.1.1 Definition of DLT Evaluable Population:

Patients enrolled in safety lead-in cohort who receive at least 4 doses and complete the DLT observation period (the first 42 days of induction treatment), unless the patient discontinued the study treatment due to a DLT.

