Grade 3 to 4 Diarrhea (Grade 3) : ≥7 stools per day over baseline; incontinence; IV fluids ≥24 hrs; interfering with ADL Colitis (Grade 3) : severe abdominal pain, medical intervention indicated, peritoneal signs Grade 4: life-threatening, perforation	Withhold avelumab for Grade 3. Permanently discontinue avelumab for Grade 4 or recurrent Grade 3 1.0 to 2.0 mg/kg/day prednisone IV or equivalent Add prophylactic antibiotics for opportunistic infections Consider lower endoscopy	If improves: Continue steroids until Grade ≤1, then taper over at least 1 month; resume avelumab following steroids taper (for initial Grade 3) If worsens, persists >3 to 5 days, or recurs after improvement: Add infliximab 5 mg/kg (if no contraindication); Note: infliximab should not be used in cases of perforation or sepsis
Dermatological irAEs		
Severity of Rash (NCI-CTCAE v4)	Initial management	Follow-up management
Grade 1 to 2 Covering ≤ 30% body surface area	Continue avelumab Symptomatic therapy (eg, antihistamines, topical steroids)	If Grade 2 persists >1 to 2 weeks or recurs: Withhold avelumab Consider skin biopsy Consider 0.5 to 1.0 mg/kg/day prednisone or equivalent. Once improving, taper steroids over at least 1 month, and resume therapy following steroids taper. If worsens: Treat as Grade 3 to 4
Grade 3 to 4 Grade 3: Covering >30% body surface area Grade 4: Life-threatening consequences	Withhold avelumab for Grade 3. Permanently discontinue avelumab for Grade 4 or recurrent Grade 3 Dermatology consult 1.0 to 2.0 mg/kg/day prednisone or equivalent.	If improves to Grade ≤1: Taper steroids over at least 1 month; resume avelumab following steroids taper (for initial Grade 3)

	Add prophylactic antibiotics for opportunistic infections	
Pulmonary AEs		
Grade of Pneumonitis (NCI-CTCAE v4)	Initial management	Follow-up management
Grade 1 Radiographic changes only	Consider withholding avelumab therapy Monitor for symptoms every 2 to 3 days Consider Pulmonary and Infectious Disease consults	Re-assess at least every 3 weeks If worsens: Treat as Grade 2 or Grade 3 to 4.

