Hypopituitarism/Hypophysitis (secondary endocrinopathies)	
If secondary thyroid and/or adrenal insufficiency is confirmed (i.e. subnormal serum thyroxine with inappropriately low TSH and/or low serum cortisol with inappropriately low ACTH)
 
 Refer to endocrinologist for dynamic testing as indicated and measurement of other hormones (FSH, LH, GH/IGF-1, PRL, testosterone in men, estrogens in women) Hormone replacement/suppressive therapy as appropriate Perform pituitary MRI and visual field examination as indicated 
If hypophysitis confirmed:
 
 Continue avelumab if mild symptoms with normal MRI. Repeat the MRI in 1 month Withhold avelumab if moderate, severe or life-threatening symptoms of hypophysitis and/or abnormal MRI. Consider 	
Resume avelumab once symptoms and hormone tests improve to Grade ≤ 1 (with or without hormone replacement).
 
In addition, for hypophysitis with abnormal MRI, resume avelumab only once shrinkage of the pituitary gland on MRI/CT scan is documented.
 
Continue hormone replacement/suppression therapy as appropriate.

	
hospitalization. Initiate corticosteroids (1 to 2 mg/kg/day prednisone or equivalent) followed by corticosteroids taper during at least 1 month.
 
 • Add prophylactic antibiotics for opportunistic infections. 	
Other irAEs (not described above)		
Grade of other irAEs (NCI-CTCAE v4)	Initial Management	Follow-up Management
Grade 2 or Grade 3 clinical signs or symptoms suggestive of a potential irAE	Withhold avelumab therapy pending clinical investigation	
If irAE is ruled out, manage as appropriate according to the diagnosis and consider restarting avelumab therapy
 
If irAE is confirmed, treat as Grade 2 or 3 irAE.

Grade 2 irAE or first occurrence of Grade 3 irAE	
Withhold avelumab therapy 1.0 to 2.0 mg/kg/day prednisone or equivalent
 
Add prophylactic antibiotics for opportunistic infections
 
Specialty consult as appropriate
	
If improves to Grade ≤ 1:
 
Taper steroids over at least 1 month and resume avelumab therapy following steroids taper.

Recurrence of same Grade 3 irAEs	
Permanently discontinue avelumab therapy 1.0 to 2.0 mg/kg/day prednisone or equivalent.
 
Add prophylactic antibiotics for opportunistic infections
 
Specialty consult as appropriate
	
If improves to Grade ≤ 1:
 
Taper steroids over at least 1 month.

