- xxvii. Administration of a live/attenuated vaccine within 4 weeks prior to the first dose of study treatment, within 5 months following the administration of the last dose of study drug, or anticipation that such a live/attenuated vaccine will be required during the study.
- xxviii. Other severe acute or chronic medical conditions including immune colitis, inflammatory bowel disease, immune pneumonitis, pulmonary fibrosis or psychiatric conditions including recent (within the past year) or active suicidal ideation or behavior; or laboratory abnormalities that may increase the risk associated with study participation or study treatment administration or may interfere with the interpretation of study results and, in the judgment of the investigator, would make the patient inappropriate for entry into this study.

5. Analysis Populations

The analysis populations are defined as below.

- a. **Safety population:** All patients who receive at least one dose of combination avelumab and BCG will be included in the analyses of compliance and safety.
- b. **Biomarker population:** For biomarker analysis, the biomarker population will comprise all evaluable patients who have sufficient baseline and on-study biomarker measurements.
- c. **Evaluable population:** Evaluable patients will be defined as patients who receive at least 5 doses of intravesical BCG and avelumab IV weekly during induction treatment and complete the first post-treatment cystoscopy and/or urine cytology for tumor assessment. Patients

who discontinued study treatment due to toxicity incurred by previous therapy will be evaluated for safety analysis, but will be replaced by additional patients for the efficacy analysis.

Patients removed from study for early withdrawal or hypersensitivity reactions will be replaced if they have received less than 5 doses of study treatment during induction treatment, but will be included in the safety analysis.

Patients who do not receive at least 5 doses of intravesical BCG and avelumab IV during induction treatment will be considered unevaluable for efficacy analysis and will be replaced unless the missed doses were due to development of grade 3-4 adverse events related to study treatment.

Evaluable population will be used for the analysis of EORTC QOQ-C30 (Section 6) and antitumor measures (Section 8).

6. Patient Population Summary

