- a. The European Organisation for Research and Treatment of Cancer Quality of Life Questionnaire (EORTC QLQ-C30) functional scales, symptom scales, and global health and quality of life scale will be summarized.

7. DLT Analysis

- a. Completion of induction therapy with combined BCG + avelumab as defined as freedom from dose-limiting toxicity (DLT) preventing completion of at least 5 of 6 treatments of BCG + avelumab within 8 weeks. Dose limiting toxicity will be based on the first 6 weeks of proposed study treatment. If 0/3 patients experience a DLT, dose expansion cohort will be activated for additional 15 patients. If 1/3 patients experiences a DLT, the dose level 1 will be expanded to 3 more patients. If 1/6 patients experiences a DLT, the dose expansion cohort will be activated for additional 12 patients. If 2 or more of the 6 patients experience a DLT, the dose level -1 will be evaluated. If the combination therapy in Cohort -1 is not tolerated (2 or more patients experience a DLT), the study will be suspended for reassessment.

i. Definition of Dose limiting toxicity

1. During safety lead-in phase, Dose limiting toxicity (DLT) will be monitored during the first 6 weeks of the combination avelumab and intravesical BCG. DLTs will be defined as any and all adverse events at least possibly related to study drug which occur in the DLT evaluation period and meet the criteria below, as evaluated by the NCI-CTCAE version 5.0.
2. Note: DLTs and other toxicities will be discussed between the Principal Investigator, and the Data Safety Monitoring Committee (DSMC). The discussions are the basis for the decisions regarding dose expansion (or de-escalation) according to the rules of the protocol.
3. DLT will be classified as either hematologic or non-hematologic toxicity (assessed in accordance with the CTCAE Version 5.0 criteria).
4. The following are DLTs:
 - a. Toxicity causing greater than 2 weeks of dose delay. For example, if a subject has dose delay greater than 2 weeks due to an AE, such AE is a DLT.

- b. Grade 4 neutropenia greater than 5 days.
 - c. ALT/AST > 3x ULN with bilirubin > 2x ULN without another explanation (e.g., cholestasis).
 - d. Any Grade 3 hypersensitivity reaction is a DLT.
 - e. Grade 4 thrombocytopenia of any duration.
 - f. Grade 3 thrombocytopenia with significant hemorrhage of any duration.
 - g. Febrile neutropenia
 - h. Any non-hematological Grade ≥ 3 toxicities will be a DLT.

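### A lead-in DLT managed by a dose hold rather than discontinuation can leave the patient outside the DLT-evaluable population

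*Protocol*

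**What the plan says.** **Definition.** Protocol 5.2.1.1 defines the DLT-evaluable population as "Patients enrolled in safety lead-in cohort who receive at least 4 doses and complete the DLT observation period" (42 days), "unless the patient discontinued the study treatment due to a DLT". SAP 7.a.ii has the same rule. Neither names the drug that the 4 doses refer to.

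**What is a DLT.** Protocol 5.2.1 lists first "Toxicity causing greater than 2 weeks of dose delay". Non-hematological toxicity of Grade 3 or higher also counts, apart from listed exceptions.

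**Decision rule.** SAP 7.a: "If 0/3 patients experience a DLT, dose expansion cohort will be activated for additional 15 patients". Protocol 5.2: "If 1/6 patients experiences a DLT, the dose expansion cohort will be activated for additional 12 patients". Two or more DLTs lead to dose level -1.

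**Holds with resumption.** In Protocol 6.4.1.2, Table 4, a Grade 2 or first Grade 3 event among the other irAEs means withholding avelumab, then: "Taper steroids over at least 1 month and resume avelumab therapy following steroids taper". Initial Grade 3 colitis or rash, Grade 2 pneumonitis and Grade 2-3 creatinine increase follow the same pattern.

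**The other drug.** Under Protocol 6.4, BCG continues by default while avelumab is held for an immune-related event, but both drugs may be interrupted. Sections 6.1 and 6.4 allow a BCG interruption of up to 3 weeks (21 days).

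**Populations.** SAP section 5 opens with "The analysis populations are defined as below" and lists the safety, biomarker and evaluable populations. The DLT-evaluable population is not among them.

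**The concern.** The protocol treats withholding a drug and permanently discontinuing it as different actions throughout Tables 2 to 4, so the exception for discontinuation cannot safely be read to include holds. Yet the first DLT criterion is by construction a hold, and several Table 4 events that would be DLTs are managed by a hold with planned resumption. A patient treated exactly as the protocol directs could have a DLT and still not be DLT-evaluable.

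The definition matters because its only evident use is as the denominator of the 3+3. In the SAP it sits under item 7.a, which states that rule. Protocol 8.2.1 shows that the authors knew the safeguard: for efficacy, patients whose missed doses were due to related Grade 3-4 events are not replaced. The DLT definition has no such clause.

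The dose decision rests on 3 to 6 patients. A patient excluded this way is excluded because of a DLT, so any error favours expansion.

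**Working it through.** The documents give no DLT rate and no operating characteristics for the 3+3, so there is no stated figure to reproduce.

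**1. Inputs.** Weekly doses on Days 1, 8, 15, 22, 29 and 36; a 42-day window (Protocol 5.2); 4 doses needed (5.2.1.1); a steroid taper of at least 1 month (Table 4), taken as 28 days to favour the plan; a BCG hold of at most 21 days.

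**2. Avelumab hold, best case.** Onset is the day after dose k, improvement is immediate, and avelumab resumes 28 days later.

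| Hold after dose | Earliest resumption | Doses by Day 42, weekly make-up | Doses by Day 42, scheduled days only |
|---|---|---|---|
| 1 | 2 + 28 = Day 30 | Days 1, 30, 37: 3 | Days 1, 36: 2 |
| 2 | 9 + 28 = Day 37 | Days 1, 8, 37: 3 | Days 1, 8: 2 |
| 3 | 16 + 28 = Day 44 | Days 1, 8, 15: 3 | Days 1, 8, 15: 3 |

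The next dose is 30 - 8 = 22 days late for k = 1, and likewise for k = 2 and 3. It is still 21 days late if onset is on the dosing day. A related Grade 2 event therefore becomes a DLT by delay, and a Grade 3 event is one by grade, exceptions apart. A hold after dose 4 or later leaves at least 4 doses.

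**3. BCG hold, with weekly make-up.**
- 15 days late: Days 1, 23, 30, 37, or 1, 8, 30, 37, or 1, 8, 15, 37. That is 4 doses each time. A delay of 20 days also leaves 4.
- 21 days late, counted from the missed due date: Days 1, 29, 36, or 1, 8, 36, or 1, 8, 15. That is 3 doses each time.
- If BCG stays on its original weekly days, the first slot more than 14 days late is the 21-day one, again leaving 3.
- A 21-day hold counted from an onset before the due date, with weekly make-up, leaves 4.

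**4. Which reading loses the patient** (hold starting before dose 4).

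| 4 doses of | Table 4 avelumab hold, BCG continues | Avelumab held, BCG also held and below 4 doses | 21-day BCG hold, avelumab continues |
|---|---|---|---|
| avelumab | not evaluable | not evaluable | evaluable |
| each drug | not evaluable | not evaluable | not evaluable |
| BCG | evaluable | not evaluable | not evaluable |
| either drug | evaluable | not evaluable | evaluable |

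The text does not settle the reading. Protocol 1.5.1 (purpose of the lead-in) and the interim trigger in 10.2 count BCG doses. Sections 8.1, 8.2.1 and the completion rate in 10.2 require each drug.

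**5. Effect on the decision, if the DLT is lost.** This is an illustration with assumed DLT rates p (q = 1 - p) and an assumed single replacement patient.
- After 1 DLT in 3, P(expand) = q³ if it counts, and q + p·q³ if it is lost.
- After 2 DLTs in 6, P(expand) = 0 if both count, and q if the second is lost.

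| p | 1/3, counted | 1/3, lost | 2/6, counted | 2/6, second lost |
|---|---|---|---|---|
| 0.10 | 0.729 | 0.973 | 0 | 0.90 |
| 0.20 | 0.512 | 0.902 | 0 | 0.80 |
| 0.30 | 0.343 | 0.803 | 0 | 0.70 |
| 0.40 | 0.216 | 0.686 | 0 | 0.60 |

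**The case against.** The strongest reply is that no document removes such a DLT. Every statement of the 3+3 counts patients in whom a DLT occurs; none restricts the count to DLT-evaluable patients, and 5.2.1.1 contains no instruction to drop or replace anyone. The investigator and the DSMC discuss DLTs and other toxicities before any dose decision. This stands. A reader might infer that the plan discards these DLTs, but the text does not say so. What remains is that a definition with no other evident use gives the wrong answer when used, and that the discussions are to follow the protocol's rules.

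Second, BCG is arguably the better-supported reading of the 4 doses: the dose levels differ only in BCG, and the lead-in exists to test BCG tolerance. A reader might infer that any early immune-related hold loses the patient. On the BCG reading it does not, because BCG continues by default. This also stands, though BCG may be held as well and the reading is not stated.

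Third, the BCG route is narrow. It needs the full 21 days, or a delay over 2 weeks kept on the weekly days, whereas 6.4.2.1 advises resuming the week after a postponed instillation. Agreed.

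Fourth, the patient stays in the safety population, which 10.2 uses for the induction completion rate, so missed doses should show there. That is only a partial backstop: it does not feed the 3+3, and avelumab make-up doses on Days 1, 30, 37, 44 and 51 would still give 5 within 8 weeks.

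Finally, the percentages above assume the loss that they illustrate. They show what a lost DLT would do, not how likely one is.

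**Conclusion.** The gap in the wording is real. A hold-managed DLT that starts before dose 4 can leave the patient outside the DLT-evaluable population: with at most 3 avelumab doses on an avelumab or each-drug reading (or on other readings if BCG is also held and falls below 4 doses), or with 3 BCG doses after a 21-day hold on a BCG or each-drug reading. If 4 doses of either drug suffice, no single-drug hold does this. DLTs that end in discontinuation of study treatment are already covered by the exception.

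Loss of the DLT from the dose decision is possible, not certain. It requires the definition to be used as the 3+3 denominator, which its place in the SAP suggests but no sentence states. If it is so used, one lost DLT turns 1/3 (enrol 3 more) into 0/3 (expand by 15), or 2/6 (de-escalate) into 1/6 (expand by 12), and never the reverse. How often such holds occur cannot be estimated from the documents. This is a low-to-moderate priority correction.

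**What to change.** In Protocol 5.2.1.1 and SAP 7.a.ii, replace the exception with: *or who experience a DLT in the DLT period, whatever the number of doses received and whether treatment is held or discontinued*. In the same place, state which drug or drugs the 4 doses refer to. No separate rule on the timing of delay-based DLTs is needed, because 5.2.1 already ties the DLT to the causing adverse event and to the evaluation period.

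The cost is two short wording changes in each document, with no new data or visits. The small downside is that the dose decision may wait for a delay-based DLT to be confirmed. For holds after dose 1, 2 or 3, a delay over 2 weeks is established on Day 23, 30 or 37, inside the window. The latest case is an event after dose 6: next avelumab is due about Day 36 + 14 = 50, the delay exceeds 2 weeks on Day 65, and 65 - 42 = 23 days of waiting. That patient already has enough doses to be evaluable, so this longest wait comes from the delay criterion itself rather than from the new clause.

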5.3 Rationale for Avelumab Dose and Schedule

In this clinical trial, the avelumab dose will be 10 mg/kg administered as 1-hour IV infusions, once every week during BCG and once every two weeks between BCG. Avelumab IV 10 mg/kg Q2W is the recommended dosing regimen and has been administered to a total of 1738 patients in dose expansion phase of the Study EMR100070-001 (see BAVENCIO[®] (avelumab) U.S. Package Insert and avelumab IB for details). One additional dose regimen, 10 mg/kg once a week for 12 weeks followed by 10 mg/kg once every 2 weeks, is also being investigated in patients with non-small cell lung cancer (NSCLC). Preliminary data from the 1L NSCLC cohort of EMR100070-001 showed that approximately 80% of reported responses occurred within 12 weeks of treatment initiation, and the majority of responses appeared to be durable. It is not expected that the exposure at 10 mg/kg once every week would substantially impact the manageable safety profile currently observed with 10 mg/kg once every 2 weeks dosing (See avelumab IB for details).

5.4 Rationale for Avelumab and Intravesical BCG combination

See [section 1.5](#).

6 TREATMENT PLAN

6.1 Treatment Dose and Schedule

Patients enrolled in this study will receive combination treatment of IV avelumab and intravesical BCG. The dose level and patient number in each cohort are summarized in [Table 1](#).

Table 1 Dose levels for safety lead-in and expansion cohorts

Dose Level	Number of Patients	Avelumab	Intravesical BCG
-1 (reduced dose)	6	10 mg/kg, IV, once a week, during BCG. 10mg/kg, IV, every other week between BCG	Induction (cycle 1): BCG 33 mg, intravesical, weekly x 6 doses (weeks 1-6); Maintenance (Month 3, 6, 12): BCG 33 mg, intravesical, weekly x 3 doses.
1 (starting dose)	6-	10 mg/kg, IV, once a week, during BCG. 10mg/kg, IV, every other week between BCG	Induction (cycle 1): BCG 50 mg, intravesical, weekly x 6 doses (weeks 1-6); Maintenance (Month 3, 6, 12): BCG 50 mg, intravesical, weekly x 3 doses.*
Final dose	12 (total of 18 patients at final dose)	10 mg/kg, IV, once a week, during BCG. 10mg/kg, IV, every other week between BCG	Induction (cycle 1): BCG 50 mg (or 33 mg), intravesical, weekly x 6 doses; Maintenance (Month 3, 6, 12): BCG 50 mg (or 33 mg), intravesical, weekly x 3 doses.
One cycle=12 weeks (84 days).			
*During periods of BCG shortage, split dose maintenance therapy (1/2-1/3) can be used at the PI discretion until sufficient BCG supplies are obtained.			

Dose interruption may be allowed for up to 3 weeks (21 days) for intra-vesical-BCG or 12 weeks for avelumab treatment related grade 3-4 adverse events.

Cystoscopy will be performed at screening, and in months 3, 6, 9 and 12 as standard of cancer care (SOC).

